7. ECOG PS 0-2
8. Age ≥ 18
9. Adequate organ function, including bone marrow, renal, hepatic, pulmonary, and cardiac function based on the last assessment performed within the Screening Period, defined as:
 - a. Absolute neutrophil count (ANC) $\geq 1,000/\mu\text{L}$;
 - b. Platelet count $\geq 50,000/\mu\text{L}$, ($\geq 30,000/\mu\text{L}$ if bone marrow plasma cells are $\geq 50\%$ of cellularity);
 - c. Hemoglobin $\geq 7.5\text{g/dL}$;
 - d. Creatinine clearance ≥ 60 mL/min (assessed as glomerular filtration rate using the Cockcroft-Gault formula);

- e. Alanine aminotransferase or aspartate aminotransferase $\leq 2.5 \times$ upper limit of normal (ULN);
- f. Total bilirubin $\leq 1.5 \times$ ULN (except for patients with Gilbert's syndrome confirmed by UGT1A1 mutation);
- g. Left ventricular ejection fraction $\geq 50\%$ as assessed by echocardiography or multi-gated acquisition (MUGA) scan; and
- h. Must have a minimum level of pulmonary reserve defined as Grade <2 dyspnea and pulse oxygenation $\geq 92\%$ on room air;

10. Prior to first dose of study drug, a woman must be either:

- Not of childbearing potential: premenarchal; postmenopausal (>45 years of age with amenorrhea for at least 12 months or any age with amenorrhea for at least 6 months and a serum follicle stimulating hormone level >40 IU/L or mIU/mL); permanently sterilized (eg, bilateral tubal occlusion [which includes tubal ligation procedures as consistent with local regulations], hysterectomy, bilateral salpingectomy, bilateral oophorectomy); or otherwise be incapable of pregnancy
- Of childbearing potential and practicing 2 highly effective method of birth control at time of informed consent and will continue through study and for at least one month after final dose of study drug. Must be consistent with local regulations regarding the use of birth control methods for subjects participating in clinical studies: e.g., established use of oral, injected or implanted hormonal methods of contraception; placement of an intrauterine device or intrauterine system; barrier methods: condom with spermicidal foam/gel/film/cream/suppository or occlusive cap (diaphragm or cervical/vault caps) with spermicidal foam/gel/film/cream/suppository; male partner sterilization (the vasectomized partner should be the sole partner for that subject); true abstinence (when this is in line with the preferred and usual lifestyle of the subject)

Note: If the childbearing potential changes after start of the study (e.g., woman who is not heterosexually active becomes active, premenarchal woman experiences menarche)

- a woman must begin a highly effective method of birth control, as described above.

11. A woman of childbearing potential must have 2 negative serum (β human chorionic gonadotropin) or urine pregnancy tests during screening, the first one within 28 days prior to the first dose of study drug and the second within 24 hours prior to the first dose of study drug.

12. A man who is sexually active with a woman of childbearing potential and has not had a vasectomy must agree to use a barrier method of birth control e.g., either condom with spermicidal foam/gel/film/cream/suppository or partner with occlusive cap (diaphragm or cervical/vault caps) with spermicidal foam/gel/film/cream/suppository, and all men must also not donate sperm during the study and for 3 months after receiving the last dose of study drug.

13. Subjects must be willing and able to adhere to the prohibitions and restrictions specified in this protocol and referenced in the informed consent form (ICF).

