Dexamethasone will be administered at 40 mg once weekly on days 1,8,15 for patients 75 years old and younger and at 20 mg once weekly on days 1,8,15 for patients older than 75. Patients may stay on their currently administered steroid regimen if it does not match the above.

ATRA will be administered in a divided dose of twice daily as an oral formulation at 35.5 mg/m²/day for the phase 1b portion, then escalated to 45mg/m²/day for 3 days. The first administration of ATRA will be given in the morning, two days before the scheduled Dara infusion. The last administration of ATRA will

be given in the evening of the day that Dara was administered (days -2, -1, and 0; day 0 is the day of Dara infusion).

Treatment repeats every 28 days for at least 8 cycles in the absence of disease progression or unacceptable toxicity. Patients achieving stable disease may continue to receive treatment in the absence of disease progression or unacceptable toxicity.

After completion of the study treatment, patients are followed up at 28 days and then every 3 months for up to 12 months. Subjects will be evaluated for disease response during each cycle and at the end of study.

Adverse events (secondary endpoint) will be recorded and graded according to the National Cancer Institute Common Terminology Criteria for Adverse Events (NCI-CTCAE) (Version 5).

Tumor response, based on the investigator's assessment, will be evaluated according to the International Myeloma Working Group (IMWG) response criteria (Durie, 2006) and will be modified (mIMWG) to add criteria for MR (Kyle, 2009) (per Appendix B).

The phase 1b portion will estimate the maximum tolerated dose (MTD) by a standard 3+3 design using data collected in the dose escalation phase. MTD will be defined for each dosing level. A maximum of 2 dose levels are planned (35.5 mg/m²/day to 45 mg/m²/day). For phase 1b the maximum number of evaluable patients is planned to be 12.

The phase 2 portion will evaluate the clinical activity of Dara + Pom + Dex + ATRA. A Simon's two-stage minimax design will be used.

Analysis of biomarkers will also be explored in subjects who consent to participate in the exploratory biomarker study.

All subjects will be maintained on the Pomalidomide pregnancy prevention program (Appendix D) for the duration of the study.

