4.3. Study Duration

This study will consist of the following consecutive phases: Screening, Treatment and Follow-up.

The study will remain open to enrollment until the target subject enrollment of approximately 42 subjects has been reached. Given our current patient population we expect to complete enrollment in two years.

Each subject will be followed for up to 12 months after enrollment (unless the follow-up is shorter due to withdrawal of consent, loss to follow-up, or death).

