10.9. Pregnancy

All pregnancies or suspected pregnancies occurring in either a female subject or partner of a male subject are immediately reportable events and should be recorded on a Serious Adverse Event Report Form and be reported to Janssen Scientific Affairs, LLC **within 24 hours of becoming aware of the event..**

In the event of a pregnancy occurring in a female subject of childbearing potential or female partner of a male subject, Janssen will follow up with the clinical investigator each trimester of pregnancy and for 1 year following the birth of the infant (if applicable). Please reference the pregnancy information consent (permission) forms for data collection for additional information.

The exposure of any pregnant female (eg, caregiver or pharmacist) to Pomalidomide is also an immediately reportable event.

10.9.1. Females of Childbearing Potential:

Pregnancies and suspected pregnancies (including elevated beta human chorionic gonadotropin [β hCG] or positive pregnancy test regardless of age or disease state) of a female subject occurring while the subject is on study treatment, or within 28 days of the subject's last dose of POM or LD-Dex or within 3 months of last dose of Daratumumab, are considered immediately reportable events. Investigational product is to be discontinued immediately and the subject instructed to return any unused portion of the IP to the investigator. The pregnancy, suspected pregnancy, or positive pregnancy test must be reported to Janssen Drug Safety immediately by email, phone or facsimile, or other appropriate method, using the Initial Pregnancy Report Form, or approved equivalent form i.e. Clinical SAE Form. The female should be referred to an obstetrician-gynecologist, preferably one experienced in reproductive toxicity for further evaluation and counseling.

The investigator will follow the female subject until completion of the pregnancy and must notify Janssen Drug Safety immediately about the outcome of the pregnancy (either normal or abnormal outcome) using the Follow-up Pregnancy Report Form or approved equivalent form.

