If the outcome of the pregnancy was abnormal (eg, spontaneous or therapeutic abortion), the investigator should report the abnormal outcome as an AE. If the abnormal outcome meets any of the serious criteria, it must be reported as an SAE to Janssen Drug Safety by facsimile, or other appropriate method, within 24 hours of the investigator's knowledge of the event using the SAE Report Form or approved equivalent form.

All neonatal deaths that occur within 28 days of birth should be reported, without regard to causality, as SAEs. In addition, any infant death after 28 days that the investigator suspects is related to the in utero exposure to the POM or LD-Dex or within 3 months of last dose of Daratumumab should also be reported to Janssen Drug Safety by facsimile, or other appropriate method, within 24 hours of the investigator's knowledge of the event using the SAE Report Form, or approved equivalent form.

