2.3. Contraception

2.3.1. Female Subjects of Childbearing Potential

Females of childbearing potential enrolled in this protocol must agree to use two reliable forms of contraception simultaneously or to practice complete abstinence (True abstinence is acceptable when this is in line with the preferred and usual lifestyle of the subject. Periodic abstinence [eg calendar, ovulation, symptothermal or post-ovulation methods] and withdrawal are not acceptable methods of contraception.) from heterosexual contact during the following time periods related to this study: 1) for at least 28 days before starting pomalidomide; 2) while taking pomalidomide; 3) during dose interruptions; and 4) for at least 28 days after the last dose of pomalidomide.

The two methods of reliable contraception must include one highly effective method and one additional effective (barrier) method. If the below contraception methods are not appropriate for the FCBP, she must be referred to a qualified provider of contraception methods to determine the medically effective contraception method appropriate to the subject. The following are examples of highly effective and additional effective methods of contraception:

- Examples of highly effective methods:
 - Intrauterine device (IUD)
 - Hormonal (birth control pills, injections, implants, levonorgestrel-releasing intrauterine system [IUS], medroxyprogesterone acetate depot injections, ovulation inhibitory progesterone-only pills [e.g. desogestrel])
 - Tubal ligation
 - Partner's vasectomy
- Examples of additional effective methods:
 - Male condom
 - Diaphragm
 - Cervical Cap

Because of the increased risk of venous thromboembolism in subjects with multiple myeloma taking pomalidomide and dexamethasone, combined oral contraceptive pills are not recommended. If a subject is currently using combined oral contraception the subject should switch to another one of the highly effective methods listed above. The risk of venous thromboembolism continues for 4 to 6 weeks after discontinuing combined oral contraception. The efficacy of contraceptive steroids may be reduced during co-treatment with dexamethasone.

[Please note, the above highlighted text is applicable for protocols with dexamethasone-containing pomalidomide regimens.]

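### The minimum contraception period for women is not counted from the last daratumumab dose, so on some readings it ends about 40 to 60 days before the protocol's own 3-month pregnancy-reporting window closes

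*Combined protocol and SAP*

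**What the plan says.** Criterion 10 has the same wording in section 6.2 and in the Protocol Summary: contraception "will continue through study and for at least one month after final dose of study drug". Appendix C, section 2.3.1, deals with pomalidomide only and runs "for at least 28 days after the last dose of pomalidomide".

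Section 10.9.1 sets its windows by drug. A pregnancy is reportable if it occurs on treatment or within 28 days of the "last dose of POM or LD-Dex or within 3 months of last dose of Daratumumab, are considered immediately reportable events". The rule on later infant deaths in the same section uses the same split: "in utero exposure to the POM or LD-Dex or within 3 months of last dose of Daratumumab".

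On how long the study lasts for one patient:

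- Section 4.3: "This study will consist of the following consecutive phases: Screening, Treatment and Follow-up".
- Section 4.3 also sets a cap: "Each subject will be followed for up to 12 months after enrollment (unless the follow-up is shorter due to withdrawal of consent", with other exceptions following.
- Section 4.1 on treatment: "Treatment repeats every 28 days for at least 8 cycles in the absence of disease progression or unacceptable toxicity".
- Section 4.1 on follow-up: "After completion of the study treatment, patients are followed up at 28 days and then every 3 months for up to 12 months".

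On donation, criterion 12 bars sperm donation by all men until 3 months after the last dose. A three-month bar on egg donation appears only in the Protocol Summary, in the note for women whose childbearing potential changes during the study. The matching note in section 6.2 omits it, and neither place applies it to women who are of childbearing potential at entry.

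**The concern.** Two clocks in one protocol do not meet. The contraception minimum runs from the final dose of any study drug and is one month. The period in which the protocol wants a pregnancy reported because of daratumumab is 3 months from that drug's last dose. Nothing links them except *through study*, and sections 4.1 and 4.3 allow different end dates for that phrase. Two sites could give two women with the same dosing history different stop dates. One of those women could follow her instructions and still conceive inside the daratumumab reporting window.

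The stake is patient safety and consistent instructions. The primary endpoint, error rates and sample size are not affected.

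**Working it through.** The plan states no figure to reproduce; the check is day counting.

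**Inputs.** 28-day cycles. Daratumumab on days 1, 8, 15 and 22 in cycles 1-2, days 1 and 15 in cycles 3-6, and day 1 from cycle 7 (section 4.1). Pomalidomide on days 1-21 (section 4.1). One month after the final dose (criterion 10). 3 months after daratumumab (section 10.9.1).

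**Assumptions.** One month = 30 days, 3 months = 90, 12 months = 365. No cycle delays, the last cycle given in full, and contraception stopped as soon as the text allows.

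**Reading 1: the study ends with treatment.** Gap = 90 − [(last study-drug day − last daratumumab day) + 30].

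| Last daratumumab dose | Sum | Gap (days) | Share of 90 days | Gap by calendar dates |
|---|---|---|---|---|
| Day 1, pomalidomide to day 21 | 90 − (20 + 30) | 40 | 44% | 38-42 |
| Day 15, pomalidomide to day 21 | 90 − (6 + 30) | 54 | 60% | 52-56 |
| Day 22, or all drugs stopped the same day | 90 − (0 + 30) | 60 | 67% | 59-62 |

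A woman who completes the planned 8 cycles is on the day-1 schedule, so 40 days is her case. If other study drugs continue k days after daratumumab, the gap is max(0, 60 − k).

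**Reading 2: the study includes follow-up, capped at 12 months after enrollment (section 4.3).** Take enrollment as Cycle 1 Day 1 = day 0 and the monthly daratumumab schedule. The last cycle n starts on day s = 28(n − 1). Gap = max(0, s + 90 − max(365, s + 50)).

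| Last cycle | s + 90 | max(365, s + 50) | Gap (days) | Gap by calendar dates |
|---|---|---|---|---|
| 10 | 342 | 365 | 0 | 0 |
| 11 | 370 | 365 | 5 | 4-7 |
| 12 | 398 | 365 | 33 | 32-35 |
| 13 | 426 | 386 | 40, then constant | 38-42 |

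If enrollment precedes Cycle 1 Day 1 by 28 days, the cap falls on day 337 and each step comes one cycle earlier: 0 at cycle 9, 5 at cycle 10, 33 at cycle 11, 40 at cycle 12.

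**Reading 3: the study includes follow-up for up to 12 months after treatment (one way to read section 4.1).** Day-1 schedule: the requirement ends 20 + 365 = 385 days after daratumumab, against a window of 90. There is no gap if she stays in follow-up to month 3.

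**Early withdrawal under readings 2 and 3.** If she withdraws w days after the last daratumumab dose and only the one-month minimum is left, then on the day-1 schedule the gap is max(0, 90 − max(w, 50)): 40 days for w up to 50, 20 at w = 70, 0 at w = 90. Under reading 2 this takes w to fall before the 12-month cap.

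**Does Appendix C close the gap?** Its 28 days after pomalidomide day 21 end 48, 34 or 27 days after daratumumab on day 1, 15 or 22. The one-month rule already reaches 50, 36 or 30 days, so Appendix C adds nothing here.

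**The case against.** The best case against the point is grammatical. The rule has two limbs joined by *and*. If the study meant treatment only, the first limb would add almost nothing, because a month after the final dose already covers treatment. Section 4.3 counts Follow-up as a study phase, section 4.1 places follow-up after treatment, and Table 1 has a three-monthly column after End of Treatment. On that view a woman who stays in follow-up is covered. This stands, and it rules out any claim that every woman faces a 40 to 60 day gap.

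It does not settle the matter. Section 4.3, the section that names the phases, also caps follow-up at 12 months after enrollment and lets withdrawal shorten it. Section 10.10 describes the study period for serious adverse events as running to at least 30 days after the last dose, and section 7.6 places an end of study visit 30-40 days after the last ATRA. Those two passages are not about contraception, but a site could reasonably borrow the shorter meaning. The conflict over follow-up length is a separate defect; here it only shows that the phrase cannot carry the rule.

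Three stronger inferences are tempting, and the documents do not support them:

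- *One month is unsafe.* The 3 months in section 10.9.1 is a reporting window, and such a window may be wider than a contraception minimum. The 3 months in criterion 12 concerns sperm donation.
- *Sites have no longer instruction.* Section 7.1 defers to the daratumumab product information, and criterion 13 to the consent form. Neither was available, and either may state a longer period.
- *The 6.2 note lets a woman whose status changes use one method.* Appendix C, sections 2.3.1 and 2.5.2.1, requires two methods and has the investigator confirm this at each visit, and section 4.1 keeps all subjects on that program.

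It is also fair that a rule is hard to enforce once consent is withdrawn. It can still be explained to the woman beforehand.

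**Conclusion.** The point holds as an internal mismatch: the stated minimum is shorter than the protocol's own daratumumab pregnancy window, and whether anything else covers the difference depends on an undefined phrase. The uncovered part is about 40 to 60 of 90 days if the study ends with treatment. With follow-up capped at 12 months after enrollment, it is 0 through cycle 10 and about 40 days from cycle 13. It is 0 for a woman who stays in post-treatment follow-up to month 3. These counts assume undelayed cycles, a full last cycle and stopping at the earliest permitted date.

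The documents do not give the number of women of childbearing potential among the maximum of 42 patients, so the number affected is unknown and may be small. No harm is demonstrated. The egg-donation omission is a separate, smaller inconsistency and does not depend on how *through study* is read. Both are worth correcting because the correction is cheap. Confidence is medium, given the unseen consent text and product information.

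**What to change.** In criterion 10, in both section 6.2 and the Protocol Summary, keep the present sentence and add: *and in any case not less than 3 months after the last daratumumab dose and 28 days after the last pomalidomide dose, whichever is later*. Add this rather than substitute it: deleting *through study* could shorten the requirement for a woman followed for up to 12 months after treatment. With the added floor the gap is 0 days on every reading.

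Carry the Protocol Summary's egg-donation restriction into section 6.2 and apply it in both places to all women of childbearing potential, at entry or after a change in status, for at least 3 months after the final dose. Match the consent text. If the sponsor wants a shorter period after daratumumab, it should record the clinical reason and define *through study*.

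The cost is a wording amendment and matching consent text, with no added visits, tests or patients and no effect on the statistical design. The downside is up to about 2 more months of contraception for some women (60 days at most under the assumptions above) and none for those already covered by follow-up, plus an egg-donation restriction for women who now have none.

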6.3. Exclusion Criteria

The presence of any of the following will exclude a subject from study enrollment:

1. Major concurrent illness or organ dysfunction
2. Active GVHD requiring systemic corticosteroids in a subject who previously received allogeneic-SCT.
3. Cord compression or CNS involvement

4. Recent/Prior active malignancy requiring active therapy 2 years prior to enrollment excluding non-melanoma skin cancer.
5. Prior life-threatening hypersensitivity to daratumumab or an IMiD
6. Plasma cell leukemia
7. Pregnant or lactating females
8. Men donating sperm during study
9. Seropositive for human immunodeficiency virus (HIV)
10. Seropositive for hepatitis B (defined by a positive test for hepatitis B surface antigen [HBsAg]).
Subjects with resolved infection (ie, subjects who are HBsAg negative but positive for antibodies to hepatitis B core antigen [anti-HBc] and/or antibodies to hepatitis B surface antigen [anti-HBs]) must be screened using real-time polymerase chain reaction (PCR) measurement of hepatitis B virus (HBV) DNA levels. Those who are PCR positive will be excluded. EXCEPTION: Subjects with serologic findings suggestive of HBV vaccination (anti-HBs positivity as the only serologic marker) AND a known history of prior HBV vaccination, do not need to be tested for HBV DNA by PCR
11. Seropositive for hepatitis C (except in the setting of a sustained virologic response [SVR], defined as aviremia at least 12 weeks after completion of antiviral therapy)
12. Chronic obstructive pulmonary disease (COPD) with a Forced Expiratory Volume in 1 second (FEV1) less than 50% of predicted normal
13. Moderate or severe persistent asthma within the past 2 years, or uncontrolled asthma of any classification. Note that participants who currently have controlled intermittent asthma or controlled mild persistent asthma are allowed to participate
14. QTc > 480ms or ventricular arrhythmia on screening EKG or history of ventricular arrhythmia
15. Myocardial infarction within 6 months before randomization, or unstable or uncontrolled disease/condition related to or affecting cardiac function (e.g., unstable angina, congestive heart failure, New York Heart Association Class III-IV)
16. Received any prior anti-myeloma therapy within 14 days of planned study treatment

7. DESCRIPTION OF STUDY TREATMENTS

7.1. Description of Investigational Product

The only investigational product we will receive for this study is Daratumumab.

Daratumumab Preparation – Subcutaneous

Daratumumab-SC will be provided as a fixed-dose (1800 mg), combination drug product containing rHuPH20 drug substance (2000 U/mL) and daratumumab drug substance (120 mg/mL) in a single vial.

Daratumumab Administration – Subcutaneous

[Daratumumab should be given according to product information:

<http://www.janssenlabels.com/package-insert/product-monograph/prescribing-information/DARZALEX+Faspro-pi.pdf>

Daratumumab (1800 mg) will be administered by SC injection by manual push over approximately 3 – 5 minutes in the abdominal subcutaneous tissues in the left/right locations, alternating between individual doses. The volume of the SC solution will be 15 mL for the 1800 mg dose. . Reasons for continued observation on subsequent daratumumab injection may include but are not limited to the following: subjects with a higher risk of respiratory complications (e.g., subjects with mild asthma or subjects with COPD who have an FEV1 < 80% at screening or developed FEV1 < 80% during the study without any medical history), subjects with IRR with the first injection of study drug, subject with decreased condition on day of dosing compared to prior dosing day. The dose of daratumumab will remain constant throughout the study.

Dara-SC Dosing:

Table 2: Dara-SC dosing schedule (whether in combination or monotherapy)

Weeks	Schedule
Weeks 1 to 8	Weekly (total of 8 doses)
Weeks 9 to 24 ^a	Every two weeks (total of 8 doses)
Week 25 and onward until PD ^b	Every four weeks

^a First dose of the every-2-week dosing schedule is given at Week 9

^b First dose of the every-4-week dosing schedule is given at Week 25

All daratumumab administrations will be in an outpatient setting. Subjects will receive pre-injection medications and post-injection medication as outlined in Sections 7.2.

Vital signs should be monitored extensively on Cycle 1 Day 1 before, and after the first administration of daratumumab. For all other administrations, vital signs should be measured before the start of injection and at the end of the injection. If the subject experiences any significant medical event, then the investigator should assess whether the subject should stay overnight for observation. If the subject has

not experienced a significant medical event but is hospitalized overnight only for observation, then the hospitalization should not be reported as an SAE.

If an IRR develops, then the injection should be temporarily interrupted or slowed down. In the event of a life-threatening IRR (which may include pulmonary or cardiac events) or anaphylactic reaction, dara-SC should be discontinued, and no additional dara-SC should be administered to the participant. See Section 7.5 for instructions on the management of IRR and local ISRs.

7.2. Guidelines for Prevention and Management of Infusion Reactions:

All participants will receive the following medications 1 to 3 hours prior to each study drug administration:

- An antipyretic: paracetamol (acetaminophen) 650-1000 mg IV or PO
- An antihistamine: diphenhydramine 25-50 mg IV or PO or equivalent. Avoid IV use of promethazine.
 - After Cycle 6, if a participant has not developed an infusion-related reaction and is intolerant to antihistamines, modifications are acceptable as per investigator discretion.
- Corticosteroids (Long-acting or intermediate-acting):
 - Administer 20 mg dexamethasone (or equivalent) prior to every daratumumab infusion. When dexamethasone is the background regimen specific corticosteroid, the dexamethasone treatment dose will instead serve as pre-medication on daratumumab infusion days.
 - Dexamethasone is given orally or intravenously prior to the first daratumumab infusion and oral administration may be considered prior to subsequent infusions.
 - If the subject does not experience a major systemic administration-related reaction after the first 3 doses, consider discontinuing the administration of corticosteroids (excluding any background regimen-specific corticosteroid).

Pre-dose administration of a leukotriene inhibitor (montelukast 10 mg PO or equivalent) is optional in Cycle 1 Day 1 and can be administered up to 24 hours before infusion as per investigator discretion.

If necessary, all PO pre-infusion medications may be administered out of the clinic on the day of the infusion, provided they are taken within 3 hours before the infusion.

Post-dose Medication:

Administer post-infusion medication to reduce the risk of delayed infusion related reactions as follows:

- Consider administering low-dose methylprednisolone (≤ 20 mg) or equivalent, the day after the infusion. However, if a background regimen-specific corticosteroid (e.g. dexamethasone) is administered the day after the infusion, additional post-infusion steroids are not required, but may be considered by the investigator.
- For participants with a higher risk of respiratory complications (e.g. participants with mild asthma or participants with COPD who have an FEV1 $< 80\%$ at screening or

developed FEV1 < 80% during the study without any medical history) the following post-infusion medication should be considered:

- Antihistamine (diphenhydramine or equivalent)
- Leukotriene inhibitor (montelukast or equivalent)
- Short-acting β 2 adrenergic receptor agonist such as salbutamol aerosol
- Control medications for lung disease (e.g. inhaled corticosteroids \pm long-acting β 2 adrenergic receptor agonists with asthma; long-acting bronchodilators such as tiotropium or salmeterol \pm inhaled corticosteroids for participants with COPD)
- In addition, these at-risk participants may be hospitalized for monitoring for up to 2 nights after daratumumab administration. If participants are hospitalized, then an improvement in FEV1 should be performed and documented prior to discharge. If these participants are not hospitalized, then a follow-up telephone call should be made to monitor their condition within 48 hours after all infusions. If the participant has not experienced a significant medical event but is hospitalized overnight only for observation, then the hospitalization should not be reported as a serious adverse event. Investigators may prescribe bronchodilators, H1-antihistamines, and corticosteroids that are deemed necessary to provide adequate supportive care in the event a bronchospasm occurs after participants are released from the hospital/clinic. If an at-risk participant experiences no major infusion-related reactions, then these post-infusion medications may be waived after 4 doses at the investigator's discretion.
- Any post-infusion medication will be administered after the infusion has completed.

